**PROTOCOL TITLE**

**1. Full Title**

A Placebo Controlled Trial of Varenicline for Smoking among those with HIV/AIDS

**2. Brief Title**

Varenicline for Nicotine Dependence among those with HIV/AIDS

**STUDY SPONSORSHIP**

**1. Funding Sponsor**

National Institutes of Health

**2. Primary Sponsor**

[name].

**PROTOCOL ABSTRACT**

Among people diagnosed with HIV/AIDS, the widespread use of highly active antiretroviral therapy (HAART) has greatly improved survival rates (Palella et al., 1998) and changed the leading causes of death, from AIDS-related diseases (e.g., non-Hodgkin's lymphoma, Kaposi sarcoma), to cardiovascular disease and lung cancer (Palella et al., 2006). As such, addressing modifiable risk factors for disease mortality among those with HIV/AIDS, including tobacco use, has become a critical priority (Nahvi & Cooperman, 2009). To date, only three smoking cessation clinical trials have been conducted with those with HIV/AIDS (Lloyd-Richardson et al., 2009; Vidrine et al., 2006; Ingersoll et al., 2007) none of which investigated the efficacy of FDA-approved medications for nicotine dependence. Varenicline is an  $\alpha 4\beta 2$  nicotinic acetylcholine receptor partial agonist with greater efficacy for treating nicotine dependence than bupropion (Gonzales et al., 2006; Jorenby et al., 2006) or nicotine patch (Aubin et al., 2008; Biazzo et al., 2010; Stapleton et al., 2008). Varenicline may be particularly efficacious for treating nicotine dependence among individuals with HIV/AIDS given that depression symptoms (Cruess et al., 2003) and cognitive impairment (Lindl et al., 2010) are common in this population, increase during smoking abstinence and predict smoking relapse (Zvolensky et al., 2009; Evans & Drobis, 2009), and are significantly reduced by varenicline (Patterson et al., 2009; Smith et al., 2009; Philip et al., 2009; Rollema et al., 2009). Therefore, we will conduct a randomized, double-blind, placebo-controlled trial of varenicline with smokers with HIV/AIDS. Specifically, 310 smokers with HIV/AIDS will be randomized to varenicline plus 9 weeks of smoking cessation counseling or placebo plus 9 weeks of smoking cessation counseling. The primary outcome variable for this study will be 7-day biochemically confirmed tobacco

abstinence at weeks 12 and 24. Secondary outcomes include: prolonged abstinence to week 12, 18, and 24 (relapse defined as 7 consecutive days of self-reported smoking, after a 2-week grace period), continuous abstinence at weeks 12 and 24 (e.g., no smoking between quit day and follow-up), time to 7-day relapse (no grace period), and lapse and recovery events. The trial results may support the use of varenicline for the treatment of nicotine dependence among those with HIV/AIDS, thereby reducing tobacco-related morbidity and mortality in this population.

## OBJECTIVES

### 1. Overall Objectives

**Aim 1: Compare 12-weeks of varenicline treatment and behavioral counseling to 12-weeks of placebo treatment and behavioral counseling for treating nicotine dependence among individuals with HIV/AIDS.** Hypothesis: Varenicline and counseling will significantly increase end-of-treatment (week 12) and 24-week biochemically-confirmed 7-day point prevalence abstinence, vs. placebo and counseling.

**Aim 2: Assess effects of varenicline therapy on quality of life (QOL) and varenicline-associated side effects.** Hypothesis: QOL will be rated higher in the varenicline and counseling group vs. the placebo and counseling group, and there will be no significant differences between treatment arms in terms of the frequency of severe varenicline-related side effects.

**Aim 3: Assess changes in affect and cognitive performance as mediators of varenicline therapy's effect on quit rates.** Hypothesis: Improved affect and reduced cognitive impairment will mediate the effect of varenicline therapy on quit rates.

**Exploratory Aim: Explore participant-related variables as moderators of varenicline therapy's effect on quit rates.** To generate new hypotheses, we will explore participant-related variables as moderators of varenicline therapy's effect on quit rates, including socio-demographic (e.g., gender, race), psychiatric (e.g., depression), and medical (e.g., HIV/AIDS symptoms, method of HIV transmission) variables. Variables were selected for this analysis based on their relationship with smoking behavior (e.g., Webb et al., 2007).

## BACKGROUND

### HAART and the Changing Causes of Death among Individuals with HIV/AIDS

The advent of HAART has greatly improved survival rates for those diagnosed with HIV/AIDS (Palella et al., 1998). In 1994-1995, prior to the advent of HAART, the mortality rate among HIV/AIDS patients was 20.2-29.4/100 person years, but was reduced to 8.4-8.8 deaths/100 person years in 1997-1998, after HAART (Palella et al., 1998; Moore & Chaisson, 1999). Recent data show the mortality rate among individuals with HIV/AIDS has dropped even further to 1.3 deaths per 100 person years (Palella et al., 2006). This medical advance has increased the number of Americans living with HIV/AIDS to about one million, with about 40,000 new cases each year (CDC, 2004). Improved medical treatment, however, has also changed the leading causes of death among those with HIV/AIDS. Prior to HAART, individuals with HIV/AIDS primarily died from AIDS-related diseases (e.g., Kaposi sarcoma), but post-HAART, the leading causes of death in this population are cardiovascular disease and lung cancer (Palella et al., 2006). As such, addressing modifiable risk factors for disease mortality among those with HIV/AIDS, including tobacco use, has become a critical priority (Niaura et al., 1998; Benard et al., 2006).

### Rates of Smoking among Individuals with HIV/AIDS

Despite substantial achievements in lowering the rate of smoking in the general population from >50% in 1965 to ~20% today, recent data show that the rates of smoking in the US have remained constant over the past 5 years (CDC, 2009; 2011). One reason for this stalled decline in US smoking rates is that certain sub-groups of smokers, including those with HIV/AIDS, who show very high rates of tobacco use, have been almost uniformly excluded from tobacco cessation research (Niaura et al., 2000; Nahvi & Cooperman, 2009). As a result, rates of tobacco use among individuals with HIV/AIDS are very high. Studies show that 50-74% of individuals with HIV/AIDS are regular smokers (Burkhalter et al., 2005; Collins et al., 2001; Crothers et al., 2005; Feldman et al., 2005; Niaura et al., 1998; Benard et al., 2006).

al., 2006; Miguez-Burbano et al., 2005; Webb et al., 2007). This rate greatly exceeds the 20% prevalence rate of smoking in the general population (CDC, 2009) and exceeds rates reported for other notable clinical populations, such as cancer ([name] et al., 2003), cardiovascular (Rigotti et al., 2006), and depressed (Grant et al., 2004) patients. As such, the targeting of HIV/AIDS patients for tobacco cessation treatment is a critical priority and may help to reignite the steady decline in tobacco use rates that has been witnessed over the past half-century.

### Tobacco-Related Health Consequences for Individuals with HIV/AIDS

Continued smoking among those with HIV/AIDS can result in serious adverse health effects. Importantly, smoking by individuals with HIV/AIDS can reduce the effectiveness of HAART. Controlling for medication adherence and comorbid illicit drug use, Feldman et al. (2006) found that smokers with HIV on HAART had a significantly lower likelihood of achieving a viral or immunologic response and had a greater chance of developing a viral or immunologic failure, vs. non-smokers with HIV on HAART. Persistent smoking among individuals who are HIV+ may also increase the likelihood for progression to AIDS (Neiman et al., 1993). Further, smoking by HIV+ patients increases risk for cardiovascular disease and cancer (Bozkurt et al., 2004; Bonnet et al., 2004; Singh et al., 1996; Tirelli et al., 2000). There is also evidence that smoking among pregnant women with HIV/AIDS can increase the risk for transmission of HIV to infants (Ahmad, 1996; Burns et al., 1994; Loutfy & Walmsley, 2004; Sprauve, 1996; Turner et al., 1997). Lastly, smoking among individuals with HIV/AIDS can exacerbate HIV-related symptoms (e.g., respiratory problems, pulmonary pneumonia) and worsen overall QOL (Cui et al., 2010; Crothers et al., 2005; Turner et al., 2001; Webb et al., 2007), and increase the likelihood of death (Pines et al., 2011). Overall, as Nahvi & Cooperman (2009) note, the achievements associated with the advent and widespread use of HAART in terms of reduced mortality rates and improved QOL among those with HIV/AIDS are being jeopardized by the cardiovascular and neoplastic diseases attributable to tobacco use.

### Nicotine Dependence Treatments for Individuals with HIV/AIDS

Given the data reviewed above, it is remarkable that very few smoking cessation trials have been conducted with this population (Gritz et al., 2007; Harris, 2010; Nahvi & Cooperman, 2009). One randomized trial with 95 patients (Vidrine et al., 2006) compared standard smoking cessation treatment (behavioral counseling and nicotine replacement therapy; NRT) to standard smoking cessation treatment plus proactive cell-phone counseling. Though this study found higher quit rates with the addition of the cell-phone counseling, the findings require replication with a larger sample and relying on cell phones to provide treatment may be a barrier to translating these results broadly across HIV/AIDS clinics. The second trial compared self-help smoking cessation plus NRT to motivational interviewing plus NRT (Ingersoll et al., 2007). This trial included only 40 smokers and found no difference in quit rates across groups. A third, larger trial ( $n = 444$ ), compared NRT and standard behavioral counseling to NRT and counseling to enhance quit motivation (Lloyd-Richardson et al., 2009); no significant differences in quit rates between the arms were detected.

As such, as of yet, there is no demonstrated efficacious treatment model for addressing tobacco use among those with HIV/AIDS and no basis on which to disseminate recommendations for the use of pharmacotherapy to treat nicotine dependence in this sub-group of smokers. Importantly, no clinical trial has formally evaluated any of the US FDA-approved medications for nicotine dependence among those with HIV/AIDS using a controlled design, including varenicline, the most efficacious treatment available for nicotine dependence (Fiore et al., 2008; [name] & Lerman, 2006). It is essential that controlled clinical trials investigate interventions that have proven efficacy in the general population in smokers with HIV/AIDS since: 1) smokers with HIV/AIDS have been almost uniformly excluded from these trials (e.g., Gonzales et al., 2006); 2) differences between smokers with HIV/AIDS and the general population of smokers in terms of psychiatric and substance abuse history/comorbidity - factors that influence smoking cessation response rates (Humfleet et al., 1999; Zvolensky et al., 2009) - diminishes the generalizability of results from clinical trials with the general population; and 3) the safety of using these medications among individuals with HIV/AIDS is currently unknown and must be explicated before broad use in HIV/AIDS clinics (Nahvi & Cooperman, 2009).

### Barriers to Quitting Smoking Among Those with HIV/AIDS

While there are limited data on specific barriers to quitting smoking that are unique to individuals with HIV/AIDS compared to the general population, two factors may be important. First, smoking cessation interventions for individuals with HIV/AIDS may need to address psychiatric history/comorbidity, most commonly depression and dysthymia (Nahvi & Cooperman, 2009). A large epidemiological study using a nationally representative sample found that more than a third of HIV+ patients exhibited major depression and another quarter had dysthymia (Bing et al., 2001). A meta-analysis of studies has shown that the risk for depression is 2-times greater if one is diagnosed with HIV/AIDS, compared to unaffected individuals (Ciesla & Roberts, 2001) which may be an under-estimate of risk (Asch et al., 2003). Symptoms of psychological distress, including depression symptoms, have been shown to be a strong risk factor for relapse following successful smoking cessation in the general population (Zvolensky et al., 2009) and have been associated with lower levels of motivation to quit smoking (Burkhalter et al., 2005) and higher risk of smoking (Webb et al., 2007) among those with HIV/AIDS. Second, smoking cessation interventions for individuals with HIV/AIDS may need to address cognitive impairment, which typically includes difficulties with memory, attention/concentration, and executive function (Heaton et al., 2011). While the advent of HAART has reduced the rate of cognitive impairment among those with HIV/AIDS, several recent surveys indicate that 39%-69% of individuals with HIV/AIDS show cognitive impairment (Robertson et al., 2007; Simioni et al., 2010). In the general population, smokers use nicotine to enhance cognitive function, nicotine withdrawal increases cognitive impairment which predicts relapse, and resuming smoking ameliorates abstinence-induced cognitive impairment (Heishman, 1999; Evans & Drobis, 2009; Rukstalis et al., 2005). Consequently, nicotine dependence treatments for individuals with HIV/AIDS may show greater efficacy if they adequately address the patient's relatively high level of psychological distress and cognitive impairment.

### Varenicline for Nicotine Dependence

Varenicline, approved by the US FDA in 2006, is the most efficacious FDA-approved medication for nicotine dependence, yielding quit rates that significantly exceed those produced by bupropion (Gonzales et al., 2006; Jorenby et al., 2006) and nicotine patch (Aubin et al., 2008; Biazzo et al., 2010; Stapleton et al., 2008). Randomized clinical trials and meta-analyses indicate that 6-month quit rates for varenicline are ~30% (Gonzales et al., 2006; Jorenby et al., 2006; Cahill et al., 2011). Varenicline is an  $\alpha 4\beta 2$  nicotinic acetylcholine receptor (nAChR) partial agonist. As such, varenicline binds to the  $\alpha 4\beta 2$  nAChRs, preventing nicotine from binding and stimulating nAChRs and dopamine release. These processes reduce the rewarding effects of smoking and reduce abstinence induced withdrawal symptoms (Rollema et al., 2009). Varenicline's efficacy is also thought to be due to the drug's effects on abstinence-induced psychological distress and cognitive impairment. Several studies show that varenicline mitigates adverse psychological effects and cognitive impairment associated with quitting smoking (Patterson et al., 2009; Smith et al., 2009; Philip et al., 2009; Rollema et al., 2009; Sofuoğlu et al., 2009). The anti-depressant-like (Rollema et al., 2009) and cognitive enhancing (Loughead et al., 2010) effects of varenicline is consistent with what we know about how this medication works. Preclinical studies indicate that  $\alpha 4\beta 2$  nAChRs subtypes are critical for cognition (Levin et al., 2009) and varenicline's stimulation of these receptors improves cognitive function (Loughead et al., 2010). Likewise, animal studies indicate that the simultaneous activation and desensitization of nAChRs produced by nicotinic partial agonists like varenicline can yield antidepressant-like effects (Mineur & Picciotto, 2010), which underlies current evaluations of varenicline as a treatment for major depression. Lastly, there are efficacy and safety data for varenicline among various clinical populations, including: cardiovascular disease patients (Rigotti et al., 2010), COPD patients (Tashkin et al., 2010), smokers with comorbid alcohol (Hays et al., 2010) and cocaine (Poling et al., 2010) dependence, and smokers with comorbid affective or psychotic disorders (McClure et al., 2010; Smith et al., 2009; Philip et al., 2009). It has been shown to be safe when used for 52 weeks (Williams et al., 2007). Although there have been reports of adverse psychiatric events following varenicline use, leading the FDA to mandate a boxed warning for varenicline, and a recent meta-analysis indicated a small yet statistically significant increased risk for cardiovascular side effects (Singh et al., 2011), pooled data from efficacy trials (Cahill et al., 2009; Tonstad et al., 2010), effectiveness trials (McClure et al., 2010), and large cohort studies (Gunnell et al., 2009; Kasliwal et al., 2009) show that varenicline is safe for treating nicotine dependence, even among smokers with psychiatric comorbidity, including depression

(Stapleton et al., 2008; McClure et al., 2010; Steinberg et al., 2010). A recent meta-analysis of varenicline trials concluded that there was insufficient evidence to associate varenicline use with serious adverse neuropsychiatric events such as depression or suicidal thoughts/behavior but that additional trials testing varenicline with smokers with a range of comorbidities is needed (Cahill et al., 2011). Following a large-scale trial supporting the safety of varenicline for smoking cessation among those with and without a current psychiatric disorder (Anthenelli et al., 2016), the FDA removed the boxed warning on varenicline in December 2016.

## CHARACTERISTICS OF THE STUDY POPULATION

### 1. Target Population

Three hundred ten adult male and female smokers 18 years of age or older who have been diagnosed with HIV/AIDS (identified through the UPENN CFAR Clinical Core, UPHS PennChart reviews and community-based HIV/AIDS organizations and events) and smoke at least 5 cigarettes per day will complete the study.

At PENN, a previous nicotine patch trial recruited a sample comprised of 45% women and 16% racial/ethnic minorities ([name] et al., 2010b). A separate PENN smoking cessation trial that used targeted efforts to recruit minority smokers had a sample comprised of 55% women and 52% racial/ethnic minorities ([name] et al., 2011). The UPENN CFAR Clinical Core population is 78% African American and 4% Hispanic American.

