### 3. Key Inclusion Criteria

Eligible subjects will be males and females:

1. 18 years of age or older who self-report smoking at least 1 cigarette (menthol and non-menthol) per day, on average.
2. Diagnosed with HIV infection and exhibiting viral load of  $\leq 1000$  copies/mL within the last 6 months.
3. Exhibiting CD4+ count of  $\geq 200$  cells/mm^3 within the last 6 months.
  1. If the participant has not had a CD4+ count test completed in the last 6 months, an older result ( $\geq 200$  cells/mm^3) may be used if evidence is provided that all subsequent viral loads results are  $\leq 1000$  copies/mL.
4. Able to use varenicline safely, based on a medical evaluation including medical history and psychiatric evaluation.
5. Residing in the geographic area for at least 7 months.
6. Women of childbearing potential (based on medical history) must consent to use a medically accepted method of birth control (e.g., condoms and spermicide, oral contraceptive, Depo-Provera injection, contraceptive patch, tubal ligation) or abstain from sexual intercourse during the time they are taking study medication and for at least one month after the medication period ends.
7. If current or past diagnosis of bipolar disorder (I, II, or NOS), eligible if:
  - a. No psychotic features
  - b. MADRS: total score  $\leq 8$  (past 4 weeks), suicidal item score  $\leq 1$  (past 4 weeks)
  - c. Y-MRS: total score  $\leq 8$  (past 4 weeks), irritability, speech content, disruptive, or aggressive behavior items score  $\leq 3$  (past 4 weeks)
  - d. No psychiatric hospitalization or Emergency Room visits for psychiatric issues in the past 6 months

- e. No aggressive or violent acts or behavior in the past 6 months
- 8. Able to communicate fluently in English.
- 9. Capable of giving written informed consent, which includes compliance with the requirements and restrictions listed in the combined consent/HIPAA form.

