## STUDY PROCEDURES

### *1. Procedures*

#### *Subjects*

Subjects will be 310 smokers who have been diagnosed with HIV/AIDS, meet study eligibility criteria, and provide written consent to participate in this between-subject trial.

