## **2. Statistical Analysis**

### **Power**

Power is provided for the primary aims since the exploratory aim is hypothesis generating. Power calculations were all approximated as t- or z-tests (2-sided,  $\alpha = .05$ ), and conducted using PASS Software (Power and Sample Size, NCSS Software, Kaysville, UT).

Aim 1: The primary analysis is a comparison in week 12 and 24 cotinine-confirmed 7-day point prevalence quit rates between placebo and varenicline. For the week 12 comparison, we based our sample size selection on the expectation that quit rates in the placebo and varenicline arms would approximate those reported in past varenicline trials with the general population of smokers (i.e., placebo = 21.2%; varenicline = 50.3%; Gonzales et al., 2006). With a sample of 310, we have >90% power to detect a significant effect between our treatment arm. Notably, we have 80% to detect a difference in week 12 quit rates if the difference between treatment arms is as small as 15%, not 29% as found in Gonzales et al. (2006), since the effect for varenicline may be smaller in this sub-group of smokers. For the week 24 comparison, we based our sample size on the expectation that the quit rate in the placebo arm would be 14.5%, vs. 33.5% for varenicline (Gonzales et al., 2006). In this case, we have 85% power to detect a significant difference between treatment arms. However, we have 80% power to detect a difference between treatment arms if the treatment arm difference is only 15%, not the 19% reported in Gonzales et al. (2006), since the effect for varenicline may be smaller in this sub-group of smokers. Even though it may appear that we are over-powered for Aim 1, we require the proposed sample to conduct the non-inferiority analyses for Aim 2.

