**6. Risk/Benefit Assessment**

There is minimal risk for serious adverse events. The treatments and procedures used in this study have been shown to be relatively safe. Varenicline has also been studied in several clinical trials and shown to be safe and efficacious. Nevertheless, there are risks in participating in this trial, which are described above.

However, the risks of participating in this trial are offset by the potential benefits for participants and society. Participants who enroll in this trial will benefit from the knowledge that they are contributing in an important way to potentially furthering scientific knowledge concerning ways to improve treatment for smokers with HIV/AIDS. All smokers will receive behavioral counseling for smoking cessation. Half of the sample will receive varenicline. The trial results may support the use of varenicline for the treatment of nicotine dependence among those with HIV/AIDS, thereby reducing tobacco-related morbidity and mortality in this population.

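### The smoking-rate threshold is 5 cigarettes per day in the target-population text but 1 per day in the inclusion criteria, so the eligible population is broader than the one described

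*Combined protocol and SAP*

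**What the plan says.** Two sections under Characteristics of the Study Population give a smoking rate.

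- **1. Target Population** describes 310 adults with HIV/AIDS who "smoke at least 5 cigarettes per day will complete the study".
- **3. Key Inclusion Criteria**, item 1, covers adults "who self-report smoking at least 1 cigarette (menthol and non-menthol) per day, on average".

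The exclusion criteria set no minimum smoking rate. The Subjects paragraph under Study Procedures restates no rate and refers back to the criteria: "Subjects will be 310 smokers who have been diagnosed with HIV/AIDS, meet study eligibility criteria".

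Current smoking rate is recorded at baseline (Demographic and Smoking History). The Aim 1 analysis is a mixed effects logistic regression with terms for time-point and treatment arm and a possible few unnamed covariates. The Data Analysis section adds covariates that turn out to be related to treatment arm or to completion of follow-up. Baseline cigarettes per day is not named as a covariate in either place.

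**The concern.** A smoking-rate floor decides who may enter a cessation trial and whom its result describes. Here the protocol gives two floors for the same 310 people. Anyone smoking at least 1 but fewer than 5 cigarettes per day passes one and fails the other.

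Three things depend on the answer:

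- **Screening and audit.** Staff working from the numbered list would enrol such a person. A monitor working from the target-population sentence could record the same person as a deviation.
- **Reporting.** A report that takes its population description from the Target Population section would say 5 or more per day, while the criteria allow lighter smokers in.
- **Interpretation.** If lighter smokers are admitted, the sample covers a wider range of baseline smoking than described, and the plan does not commit to accounting for that range in the primary model.

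**Working it through.** The point rests on two text thresholds, so there is no figure of the plan's own to reproduce. The check sets the passages side by side and looks for anything that reconciles them.

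**1. The two statements**

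| Section | Threshold | Type of text |
|---|---|---|
| 1. Target Population | at least 5 per day | description of the 310 participants |
| 3. Key Inclusion Criteria, item 1 | at least 1 per day, on average, by self-report | numbered entry criterion |

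Both are current text in one protocol version. Neither sits in an amendment history.

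**2. Who is affected**

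| Cigarettes per day | Inclusion criterion 1 | Target Population |
|---|---|---|
| fewer than 1 | not eligible | outside |
| at least 1, fewer than 5 | eligible | outside |
| 5 or more | eligible | inside |

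The statements disagree only in the middle row, and always in the same direction: the criteria are the wider of the two.

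**3. Does any other text settle it?**

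- The exclusion criteria (smoking behaviour, alcohol and drugs, medication, medical, suicide history, general) contain no minimum rate that would raise the floor from 1 to 5.
- The abstract, 2. Accrual and the Subjects paragraph refer to smokers without giving a rate.
- 7. Subject Recruitment has records judged against the inclusion and exclusion criteria, and the Subjects paragraph does the same for participants. This indicates which text staff are likely to apply. It does not explain the figure of 5.
- Nothing presents 5 per day as an expected average, a recruitment goal or a superseded rule.

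**4. Which analyses would change?**

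The primary analysis is by intent to treat. The named alternatives are a completers-only analysis and one excluding participants lost to follow-up through death. None selects participants by smoking rate, so a randomised lighter smoker stays in the primary comparison under either reading. What changes is the status of that participant and the description of the population, not the validity of the randomised comparison.

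**5. Is baseline smoking rate handled in the model?**

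Not by commitment. It could enter the Aim 1 model only as one of the unnamed covariates, or if it proved to be associated with arm or follow-up. Level of nicotine dependence is named as a possible exploratory moderator, which is neither the same variable nor part of the primary model.

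**The case against.** The strongest reply is that the Target Population sentence is descriptive and is not an entry rule. The recruitment text and the Subjects paragraph point to the numbered criteria, and 2. Accrual projects numbers from them. On that reading the operating rule is clear and one sentence is merely out of step. Much of this stands: the numbered list is the natural operating rule, and that lowers the risk of inconsistent screening. It does not remove the contradiction. The sentence gives a numeric floor for the same 310 people, and a reader has no textual basis for setting it aside.

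A second reply is that smoking rate and dependence are already measured and may be adjusted for. That is true, and it keeps the remedy small, but the adjustment is optional and partly data-driven.

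Two stronger readings are tempting and should be resisted.

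- **That the wrong people were enrolled.** The documents do not show who was enrolled or how many smoked fewer than 5 per day. They support only a statement about who is eligible.
- **That the trial is underpowered because lighter smokers shift the quit rates.** The Power section takes its week 12 rates ("placebo = 21.2%; varenicline = 50.3") from a general-population trial. It allows for a smaller drug effect in people with HIV/AIDS, and it does not discuss light smokers. A power loss needs their share and their quit rates, and the documents give neither. As an illustration, assume a share s of 10–30% and a placebo quit rate q of 30–40% in that group. The placebo rate is then (1 − s) × 21.2% + s × q. It runs from 0.9 × 21.2 + 0.1 × 30 = 22.1% to 0.7 × 21.2 + 0.3 × 40 = 26.8%. With 155 per arm, two-sided 0.05 and a pooled-variance z-test, power for a 15-point difference moves from 83.5% to between 79.7% and 82.8%, close to the plan's stated 80%. Against the planned 50.3% it stays above 99%. An extreme assumption, no drug effect at all in lighter smokers, would take week 24 power from 97.8% to 82% at a 30% share and 71% at 40%, with week 12 still at 92% or more. Nothing in the documents supports that assumption.

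**Conclusion.** The contradiction is real. The eligible population under inclusion criterion 1 is wider than the population in the Target Population section by those who smoke at least 1 but fewer than 5 cigarettes per day, and no other text resolves it. The consequence is uncertainty about whether such participants are valid entrants or deviations, and about which smokers the conclusion covers.

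Its size in people is unknown, because the share of lighter smokers is not given. The finding needs no numerical assumption; it rests only on both sections being in force. It is not a finding of faulty enrolment, of inadequate power or of bias in the randomised comparison, and it does not say that either threshold is a poor choice. It should be corrected because an entry threshold must read the same wherever it appears.

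**What to change.** 1. Reconcile 1. Target Population and 3. Key Inclusion Criteria to one threshold. The sponsor should state which threshold applies, and if it changed during the trial, from when. This review does not choose between them.
2. If people smoking fewer than 5 per day are admitted, describe the population that way in the Target Population section and in the report. Name baseline cigarettes per day as a pre-specified covariate in the Aim 1 model, fixed before outcome data are unblinded for analysis.
3. Optionally, report quit rates by arm for under 5 and for 5 or more per day, as description only.

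The first step is a text correction. The second adds a sentence to the analysis plan and one model term, using a variable already collected at baseline. No new assessments or change in sample size are needed, and all three steps remain possible if recruitment has ended.

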### 2. Accrual

For this trial, we project that we will screen ~1000 HIV/AIDS patients over 54 months (allowing six months to complete follow-up), 77% of whom will be current smokers ( $n = 770$ ). Additional data indicate that upwards of three-quarters of these patients will want to quit smoking and will want to use a medication in their quit attempt (Drach et al., 2010), yielding a sample of ~575 patients to recruit. Based on past varenicline trials ([name] et al., 2011; Patterson et al., 2009) and the present inclusion/exclusion criteria, we expect ~two-thirds of these patients to be eligible for the trial ( $n = \sim 345$ ). To be conservative, given the possible health problems evident in this population of smokers, we will project  $\leq 20\%$  of participants will withdraw from the trial and  $\geq 80\%$  of subjects will complete follow-ups. As is advised in smoking cessation trials (Hughes et al., 2003), intent-to-treat will be used for primary analyses, with missing outcome data coded as smokers.

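### 310 is the number completing in one section and the number randomised in others; the last accrual step is miscalculated; and the QOL power allows for no dropout

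*Combined protocol and SAP*

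**What the plan says.** **The target.** Under Characteristics of the Study Population, Target Population, 310 adult smokers "will complete the study". The Protocol Abstract says that "310 smokers with HIV/AIDS will be randomized to varenicline plus 9 weeks of smoking cessation counseling" or to placebo with the same counselling. Under Study Procedures, the Subjects paragraph reads "Subjects will be 310 smokers who have been diagnosed with HIV/AIDS, meet study eligibility criteria, and provide written consent".

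**The accrual funnel.** The Accrual section says "we project that we will screen ~1000 HIV/AIDS patients over 54 months", "77% of whom will be current smokers" (770), and that "upwards of three-quarters of these patients will want to quit smoking and will want to use a medication in their quit attempt", which it puts at about 575. Then "we expect ~two-thirds of these patients to be eligible for the trial", printed as about 345. Withdrawal is projected at no more than 20%, so that at least 80% "of subjects will complete follow-ups". Study Duration adds a rate of about 6 subjects a month for about 54 months.

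**The analysis.** Primary analyses are intent-to-treat, with missing smoking outcomes counted as smoking. The Power section takes 310 as its sample for every aim and states no inflation for dropout.

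**The concern.** With up to 20% loss allowed, 310 randomised and 310 completing describe different trials, and the document uses both. The funnel that should show which one is feasible has an error in its final step, so it does not settle the matter.

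Aim 1 is largely shielded, because everyone randomised stays in the denominator. QOL (Aim 2) and the mediators (Aim 3) are not. The missing-data text imputes missing items within a measure and gives a rule for missing smoking status. It gives no rule for a participant whose QOL or mediator visit is missing altogether. For those analyses the stated power holds only if 310 people supply data.

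**Working it through.** **1. The funnel, reproduced step by step** (inputs from Accrual)
- Smokers: 1000 × 0.77 = 770. Matches.
- Want to quit with medication: 770 × 0.75 = 577.5, printed as about 575. Matches.
- Eligible: 575 × 2/3 = 383 (from the unrounded 577.5, 385). Printed as about 345. Does not match: 38 too low, or 10% below the product.
- 345 / 575 = 0.60 exactly, so the printed count fits 60% and not two-thirds.

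**2. Completers at the 20% bound**
- Count corrected: 383 × 0.80 = about 307 (385 × 0.80 = 308).
- Fraction corrected to 60%: 345 × 0.80 = 276.
- Loss that still leaves 310 completers: 1 − 310/345 = 10.1%, or 1 − 310/385 = 19.5%.

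**3. The two meanings of 310**
- 310 randomised: 310 × 0.80 = 248 completers at the bound.
- 310 completing: 310 / 0.80 = 388 randomised at the bound.
- Rate in Study Duration: 6 × 54 = 324 enrolled, of whom 324 × 0.80 = 259 would complete at the bound. This fits 310 as the number enrolled.

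**4. QOL power** (SD 24.5, difference 7.8, two-sided α = 0.05, equal arms assumed)

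SE = 24.5 × √(2/n per arm); power = Φ(7.8/SE − 1.96).

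| Analysed | Per arm | SE | 7.8/SE | Power (z) | Power (t) | Detectable at 80% (z / t) |
|---|---|---|---|---|---|---|
| 310 | 155 | 2.783 | 2.803 | 80.0% | 79.8% | 7.80 / 7.82 |
| 248 | 124 | 3.112 | 2.507 | 70.8% | 70.4% | 8.72 / 8.75 |

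The plan's own 80% for 7.8 points reproduces at 310 analysed.

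**5. Mediator power** (standardised effect 0.19, α = 0.0125, one-sample form as in Power)

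Power = Φ(0.19 × √n − 2.498).
- n = 310: Φ(3.345 − 2.498) = 80% (z 80.2%, t 79.7%). Reproduces the plan.
- n = 248: Φ(2.992 − 2.498) = 69% by z, 68% by t.

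The second line is a worst case only. The Aim 3 analysis centres on change from baseline to week 3, and the plan gives no figure for loss by then.

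**The case against.** **A reader might infer that the funnel cannot deliver 310 completers.** The documents do not support that. The figure of 276 needs both the 345 that disagrees with its own fraction and the full 20% loss. If the count is what is wrong, about 307 complete, which is effectively 310. The 20% is an upper bound, three-quarters is given as a minimum, and the other inputs are approximate. Subject Recruitment also lists further sources to draw on if accrual is slow, so the funnel is a projection and not a ceiling. This objection stands in full.

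**The intended meaning of 310 can be recovered.** Two sections and the monthly rate point to the number enrolled, and Target Population may simply be loosely worded. That is probably right, and it is the reading adopted in the fix. But it is also the reading under which the Power section lacks a dropout allowance, so it does not dispose of the point.

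**Only secondary aims are touched, and late.** Aim 1 keeps its denominator, and the primary comparison is not undermined by this point. It would also be wrong to apply 248 as the expected number for mediators, since the loss figure is not a week-3 figure. Version 19 is dated after the projected completion date, so correcting the forecast has little operational value. These limits stand. The QOL power statement still needs correcting, because it bears on how a null QOL result is read.

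**Conclusion.** Three things are wrong as written.
- **Meaning of 310.** Target Population conflicts with the Protocol Abstract and the Subjects paragraph. At the plan's own bound the gap is up to 62 completers (310 against 248), or 78 randomised (388 against 310).
- **Eligible count.** It is understated by about 38, or else the fraction should be about 60%. The documents do not say which.
- **QOL power.** The stated 80% for 7.8 points assumes 310 analysed. If 310 are randomised and 20% are lost, power is about 70%, or 80% for about 8.75 points.

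The QOL figures rest on the plan's SD of 24.5, equal arms, loss at the upper bound and no recovery of information from partly observed participants. With smaller loss, power lies between 70% and 80%. The funnel figures assume that every eligible patient enrols. For the mediators the most that can be said is that power would be about 68% if week-3 loss were as high as 20%.

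**What to change.** - **Target Population:** say that 310 will be randomised, with at least about 248 expected to complete at the 20% withdrawal bound. Use 310 as the number randomised throughout.
- **Accrual:** change about 345 to about 383, or change two-thirds to about 60%, whichever input the sponsor confirms.
- **Power, Aim 2:** state QOL power as 80% for 7.8 points with 310 analysed, falling to about 70% at 248 (or 80% for about 8.75 points).
- **Power, Aim 3:** give mediator power at the number expected to have week-3 data, with 248 shown only as a worst case (about 68% for an effect of 0.19 at α = 0.0125).

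The cost is a few restated figures and a less favourable power statement for the secondary aims. No patients, visits or procedures are added.
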